$$Var(Y_{ijk}) = \sigma^2 = \sigma_P^2 \mathbf{1}_{\{k \neq 0\}} + \sigma_{BS}^2 + \sigma_{WS}^2$$

Note that we allow the improvement in CAPS total score to vary at these three post-treatment timepoints in the mixed effects model; the contrast or estimate statement in SAS will be used to estimate and compare the primary outcome between PE and CPT. Although we anticipate the improvement in CAPS total score established in the treatment course will sustain for 6 months for both PE and CPT, this more flexible model allows the possibility of worsening PTSD symptoms after study treatment is discontinued and the possibility of improving PSTD symptoms if participants initiate other PTSD treatments post study treatment.

2. Sample size ignoring therapist effect

For an individual participant with CAPS total score measured at pre-treatment and at *t* post-treatment timepoints, the variance of the primary outcome for this participant is

$$\tau^2 = \sigma_P^2 + \frac{\sigma_{WS}^2}{t} + \sigma_{WS}^2,$$

where σ_P^2 is the variance of the therapist random effect and σ_{WS}^2 is the within-subject variation of the CAPS total score. Under the simplified assumptions that all study participants have CAPS total score measured at pre-treatment and at *t* post-treatment timepoints and that each study participant is treated by a different therapist, the sample size per treatment group needed to achieve power *1-β* to detect a mean difference of $\Delta \mu$ between PE and CPT in the primary outcome, using a two-sided t-test with two-sided significance level *α* is:

$$n = \frac{2(z_{1-\alpha/2} + z_{1-\beta})^2}{(\Delta \mu/\tau)^2}$$

The estimated variance components from CSP #494 are $\sigma^2 = 678$, $\sigma_P^2 = 36$, $\sigma_{BS}^2 = 504$, $\sigma_{WS}^2 = 174$, and thus $\tau = 16.4$ when t=3 and $\tau = 17.2$ when t=2. Therefore if we assume all participants have complete follow-up CAPS total score (t = 3), it requires a total of 452 participants (226 per group) to have 90% power to detect a difference of $\Delta \mu = 5$ between PE and CPT in the primary outcome. If each participant has only 2 post-treatment CAPS total scores (t = 2), it requires 498 participants (249 per group) to have 90% power.

3. Adjusting for correlations due to therapist

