In this study, each therapist will deliver either PE or CPT to a number of study participants. Although the treatment will be delivered on an individual basis, observations from the participants treated by the same therapist are likely to be correlated. Assuming each therapist treats *m* study participants, the sample size obtained under the independent participants assumption (in **Section X.B.2**) needs to be inflated by the following inflation factor *f* to retain the same power (Campbell et al., 2007; Machin et al., 2009):

$$f = 1 + (m-1)\rho,$$

where ρ is the intraclass correlation due to therapist, or equivalently the correlation between the primary outcomes from two individuals receiving treatment from the therapist. When each of these two individuals has *t* post-treatment measurements, ρ can be expressed as

$$\rho = \frac{\sigma_P^2}{\tau^2} = \frac{\sigma_P^2}{\sigma_P^2 + \frac{\sigma_{WS}^2}{t} + \sigma_{WS}^2}.$$

Using the variance estimates from CSP #494, $\rho = 0.134$ when t = 3. The Planning Committee determined that it is reasonable to assume each therapist will deliver either PE or CPT to eight participants over the course of the study (m = 8). It follows that $f = 1 + (8-1)^* 0.134 = 1.94$. Hence a total of 878 participants (439 per group) is needed to provide 90% power to detect $\Delta \mu = 5$ in the primary outcome (assuming each participant has baseline CAPS total score and complete follow-up CAPS total score at immediate post-treatment and at 3 and 6 months post treatment) as shown in **Table X.1** below.

Table X.1 Total sample size needed for a range of parameter values.

Δμ	t	τ	Δμ/ τ	ρ	f	Power	
						85%	90%
5	3	16.4	0.30	0.13	1.94	750	878
5	2	17.2	0.29	0.12	1.85	788	920
5	1	19.6	0.26	0.09	1.66	916	1072

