We anticipate some participants may not have complete follow-up CAPS total scores at the three post-treatment timepoints. If each participant has t = 2 follow-up CAPS total score (instead of 3), then $\rho = 0.121$, f = 1.85, and it requires a total of 920 participants (460 per group) to provide 90% power to detect $\Delta\mu$ =5 in the primary outcome, using the same values of variance components as above. In CSP #494, about 75% of participants had all follow-up CAPS total scores, and the average number of follow-up CAPS total scores is 2.45. In this study we expect a higher proportion of participants to have complete follow-up CAPS total score because CAPS assessment will be conducted over telephone, not requiring a clinical visit from the participant. To protect against missing CAPs total scores, potential deviations of the various variances from the assumed values and possible deviation that some therapists will treat more than 8 participants, we plan to randomize 900 participants in this study (450 per group). See

Table X.2 for the power of the study (with sample size of 900) to detect $\Delta \mu$ = 5 or 4 for a range of *r* and ρ values (the number of participants treated by each therapist is fixed at 8).

Δμ	ρ	τ =16	τ =17	τ =18	τ =19	τ =20
5	0.100	95%	92%	89%	86%	82%
	0.120	93%	90%	87%	83%	79%
	0.134	92%	89%	85%	81%	77%
	0.150	91%	87%	83%	79%	74%
4	0.100	82%	77%	72%	68%	63%
	0.120	79%	74%	69%	64%	60%
	0.134	77%	72%	67%	62%	58%
	0.150	74%	69%	64%	60%	55%

Table X.2 Power of the study to detect for $\Delta\mu$ =5 or 4 for various vales of τ and ρ .

4. Alternative derivation

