The study does not plan to conduct interim analyses to allow early stopping of the study for efficacy (when there is sufficient evidence that one treatment is superior to the other treatment) or for futility (when it is futile to establish a statistical significant difference at the end of the trial). The rationales are (1) both PE and CPT are effective treatments for PTSD, so there are no ethical concerns in continuing the study even when it is unlikely to establish a statistical significant difference at the end of the trial; (2) even when there are treatment differences between PE and CPT, the differences are not likely to alter the VA policy to make all evidence-based treatment available to PTSD patients based on interim analysis results; (3) it is important from a public health, policy, and scientific perspective to collect sufficient data on the secondary outcomes to support findings in the primary outcome, in the hope that the totality of the evidence will be able to provide guidance to or change clinical practice; (4) it allows us to examine the impact of patient preference on treatment effectiveness, which is one of the key elements in personalized medicine.

The DMC agrees with what is written in the protocol (as stated above) that there should be no early stopping for efficacy or futility; however, DMC requested CSPCC to

calculate means and standard deviations of outcome data by treatment group in each DMC report and also carry out the treatment comparisons.

- E. Levels of clinical and statistical significance (one-tailed or two-tailed)
 The level of statistical significance is two-tailed tests at p<0.05, with 90% power. The Planning Committee considered an effect size of 0.25 to be a clinically meaningful difference, that translates to a Δµ≈5 points difference in the primary outcome.
- F. Methods for handling more than two treatment groups multiple comparison methods Not applicable. This study has two treatment groups to compare.
- G. Primary and secondary outcomes See Table I.1 and Section II.H.3 for details.
- H. Hypotheses to be tested and analyses to be performed to meet the trial objectives
 - 1. Baseline comparability

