Secondary analysis: We will provide point estimates and pointwise 95% confidence intervals for the mean differences in the CAPS total scores at the three post-treatment timepoints as well as the mean differences in changes of CAPS total score from baseline at these post-treatment timepoints. We will also compare the longitudinal profiles of CAPS total score (including the mid-treatment and post-treatment scores) between PE and CPT by testing the treatment by time interaction. When data permits, we will explore site variations in treatment effect and also explore the impact of different covariance variance structures (e.g., allowing the variance of therapist random effect to differ by treatment or allowing certain variances or covariances to vary by time). Although we anticipate minimum missing data in CAPS total score, we will perform analyses to examine the missing data patterns and the impact of missing data.

As in CSP #494, we will use the CAPS to derive additional measures of clinical outcomes: response (defined as at least 10-point improvement in severity), loss of diagnosis (response plus no longer meeting DSM symptom criteria), and remission (loss

of diagnosis plus the DSM-5 score that corresponds to a DSM-IV severity score < 20). The observed proportions and their 95% confidence intervals will be provided for each treatment group at each of the follow-up timepoints. Chi-square tests will be used to compare these outcomes between the two treatment groups.

3. Secondary objective

The secondary objective is to compare the effectiveness of PE and CPT for reducing the severity of comorbid mental health problems and service utilization and improving functioning and quality of life.

These secondary outcome measures, listed in Table II.1 below, will be compared between PE and CPT to support the comparative effectiveness of these two treatments in CAPS total score. Except for Brief Addiction Monitor and certain service utilization outcomes (which are categorical measures), all other secondary outcomes are continuous measures and will be analyzed in a manner similar to CAPS total score as described above. Generalized linear mixed effects models (SAS PROC GLIMMIX) will be used to compare the longitudinal profiles of the categorical measures between PE and CPT. Generalized estimating equations may also be used. We do not plan to adjust for multiple comparisons due to the supportive nature of these secondary outcomes.

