Treatment Session 1	0-30 days after randomization
Treatment Session 2-14*	7-21 days after previous session
Mid-Treatment Assessment (Session 6)	0-14 days after session 6
Post Treatment Assessment	0-14 days after final treatment session
3-month Assessment	3 months ±2 weeks after final treatment session
6-month Assessment	6 months ±2 weeks after final treatment session

* The site SC and therapist will make sure Treatment Session 7 is scheduled after the "Mid-Treatment Assessment (session 6)" visit.

K. Rules for handling windows with more than one visit

Visit follows sequentially from previous visit. Thus, it won't be an issue for this study. If a visit is late in the follow-up phase, the late visit will be assigned to the visit with the closest target date.

L. Data inclusion/exclusion decision rules

Plan to use the data from all randomized participants in the analyses, regardless of the number of sessions they have completed. However, for sites with questionable data the study Executive Committee and Data Monitoring Committee will make recommendation to CSR&D Director whether to exclude the data from analyses or not.

M. Definition of compliance

Treatment compliance and termination will be reported and monitored. Regardless of their treatment compliance levels, the data from all participants will be used for analyses.

N. Methods for handling multiple observations

Appropriate methods for analyzing repeated measures data (e.g., mixed effects models, generalized estimating equations) as described in Sections II.H.2 and II.H.3 above.

- O. Use of baseline variables See Section II.H.1 above.
- P. Rules for calculation of derived variables See Section II.H.2 above.
- Q. Use of covariate data See Sections II.H.4 and II.H.5 above.
- R. Rules for stopping the trial, and allowance for them in the analysis See Section II.D.2 above.

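### Response, loss of diagnosis and remission have no rule for a missing CAPS; the natural available-case reading can bias the PE–CPT comparison when missingness depends on outcome and the arms differ in its rate or its mechanism

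*SAP*

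**What the plan says.** SAP II.H.2 and Protocol X.D.2 derive three binary outcomes from the CAPS and plan this summary: "The observed proportions and their 95% confidence intervals will be provided for each treatment group at each of the follow-up timepoints". Chi-square tests then compare the arms. No denominator is defined. SAP II.P sends the reader back to II.H for derived-variable rules, and II.H.2 has none for a missing score.

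Other provisions come close without covering these outcomes:

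- The linear mixed model, which uses partial follow-up, is for CAPS total score. Generalised linear mixed models or GEE are planned for the categorical outcomes in SAP Table II.1 (Protocol Table X.3), which does not list these three.
- SAP II.L states: "Plan to use the data from all randomized participants in the analyses, regardless of the number of sessions they have completed".
- SAP II.H.2 promises to examine missing-data patterns and impact for CAPS total score. SAP II.S (Protocol X.F) offers interpolation and multiple imputation as robustness checks, completer analyses, and non-ignorable sensitivity analyses if large fractions are missing. It names no outcome and sets no threshold.
- On CSP #494, Protocol X.B.3 reports that about 75% of participants had every follow-up CAPS and that "the average number of follow-up CAPS total scores is 2.45", out of three. It expects better completeness here because the CAPS is done by telephone, but gives no figure.

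**The concern.** A chi-square test needs a status for everyone it counts. Where no rule assigns one, a person without a CAPS at a visit falls out of that visit's table. Someone with post-treatment and 3-month scores but no 6-month score is dropped at 6 months, although the earlier scores say much about the likely status.

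An observed proportion is unbiased if being observed is unrelated to outcome within the arm. The primary mixed model, on the same instrument, needs only that missingness be explained by the data it includes. The two analyses could therefore disagree for reasons of missing data alone. These three outcomes put the CAPS result in terms a clinician can read directly, so a spurious PE–CPT difference here could be taken at face value.

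Arm-specific loss is conceivable on the protocol's own evidence. Section I.C.4 reports that, in the earlier head-to-head trial, higher baseline anger went with dropout from PE but not from CPT. That is dropout from treatment, not a missing CAPS, and Section I.C.2 cites no difference in overall dropout between types of therapy.

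**Working it through.** **1. The plan's own figure.** Protocol X.B.2 gives variance components of 36 (therapist) and 174 (within subject). With three follow-up scores, τ² = 36 + 174/3 + 174 = 268, so τ = 16.4. Per group, n = 2(1.960 + 1.282)² × 268 / 5² = 225.3, rounded up to 226. With ρ = 36/268 = 0.134 and eight participants per therapist, f = 1 + 7 × 0.134 = 1.94, and 226 × 1.94 gives 439 per group. This agrees with "Hence a total of 878 participants (439 per group) is needed to provide 90% power to detect" a 5-point difference. No sample size, power or missing rate is stated for the binary outcomes.

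**2. Share missing per visit.** 1 − 2.45/3 = 0.183, about 1 in 5.5. Of 900 that is 165, leaving 735 observed (367.5 per arm).

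**3. Information set aside.** A change score from baseline has variance 36 + 174 + 174 = 384. Two change scores on the same person share 36 + 174 = 210, so they correlate at 210/384 = 0.55. With normal scores and an assumed 60% response rate, a post-treatment responder has about a 75% chance of responding at 6 months and a non-responder about 38%.

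**4. Bias under the null.** Let p be the true rate, equal in both arms, and r the share observed in an arm. Let q1 and q0 be the chances of being observed for responders and non-responders, with odds ratio OR = [q1/(1 − q1)]/[q0/(1 − q0)] and p·q1 + (1 − p)·q0 = r. The observed proportion is p·q1/r. Example: p = 0.5, r = 0.817 and OR = 2 give q0 = 0.766 and q1 = 0.867, so the observed proportion is 0.5 × 0.867/0.817 = 53.1%.

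Type I error comes from the normal approximation to the chi-square test with 450 randomised per arm and no therapist clustering, which isolates the missing-data effect. Example: a 3.1-point bias against a standard error of √(2 × 0.25/367.5) = 3.7 points gives 13.5%.

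Results at p = 50% (differences taken before rounding):

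| Missing, arm 1 / arm 2 | OR, arm 1 / arm 2 | Observed, arm 1 / arm 2 | Difference (points) | Type I error |
|---|---|---|---|---|
| 13.3% / 23.3% | 1 / 1 | 50.0% / 50.0% | 0 | 5% |
| 18.3% / 18.3% | 2 / 2 | 53.1% / 53.1% | 0 | 5% |
| 18.3% / 18.3% | 3 / 3 | 54.8% / 54.8% | 0 | 5% |
| 13.3% / 23.3% | 2 / 2 | 52.2% / 54.0% | +1.7 | 7.5% |
| 13.3% / 23.3% | 3 / 3 | 53.4% / 56.1% | +2.7 | 11% |
| 18.3% / 18.3% | 1 / 2 | 50.0% / 53.1% | +3.1 | 13.5% |
| 18.3% / 18.3% | 1 / 3 | 50.0% / 54.8% | +4.8 | 25% |

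Over assumed true rates of 30–60%, unequal and outcome-related missingness gives +1.4 to +2.7 points, and a relation that differs by arm gives +2.4 to +4.9.

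**5. Fewer missing.** Take the last two rows at p = 50% with 10% missing in each arm. OR = 2 gives q0 = 0.870 and q1 = 0.930, hence 0.5 × 0.930/0.90 = 51.7%, a difference of +1.7. OR = 3 gives q0 = 0.854 and q1 = 0.946, hence 52.6% and +2.6.

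**6. Missing counted as failure.** With p = 50% and uninformative missingness of 13.3% v 23.3%, the proportions become 0.5 × 0.867 = 43.3% and 0.5 × 0.767 = 38.3%. That is a spurious 5.0-point difference, rejected 33% of the time, while the observed-case test stays at 5%.

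**7. What imputation has to work with.** In CSP #494 the incomplete 25% averaged (2.45 − 0.75 × 3)/0.25 = 0.8 of 3 scores. Missing visits number 3 − 2.45 = 0.55 per person. The share without any follow-up CAPS lies between 5% of participants (if nobody had exactly two scores) and 15% (if nobody had exactly one). Those people account for 0.15/0.55 = 27% to 0.45/0.55 = 82% of missing visits.

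**The case against.** The strongest reply is that missing data are already addressed. SAP II.S is general and could cover these outcomes, II.H.2 promises to examine the impact of missing CAPS scores, outcome collection is attempted after treatment stops, and these are supportive analyses. All of that stands. What it leaves open is the main result: II.S uses imputation only to test robustness and names no outcome, and interpolation cannot fill a missing final visit.

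The word for the proportions may also mean raw as opposed to model-based, so available-case analysis is an inference and not a stated rule. The denominator is undefined on either reading.

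A reader might infer more than the documents support:

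- **That the all-randomised rule is abandoned.** SAP II.L turns on sessions completed, and SAP II.M on treatment compliance. A score never collected breaches neither. The gap is that II.L supplies no method for such a person.
- **That unequal missingness, or outcome-related missingness, is enough by itself.** The first three rows of the table show no difference and 5% error.
- **That 18.3% of this trial's participants will be missing at each visit.** That is the CSP #494 rate, and Protocol X.B.3 expects better.
- **That bias would be about 4.4 points with 23% false positives.** This follows at 60% response if, in one arm only, the missing respond 20 points less often than that true 60%: 0.18 × 20/0.82 = 4.4. If the gap is measured from those observed, it is 0.183 × 20 = 3.7 points and about 17%. Either way the mechanism must be specific to one arm.

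**Conclusion.** The concern holds in a limited form. The plan gives three CAPS-derived outcomes a per-visit test with no missing-data rule. Read naturally, that analysis discards each person's other scores and rests on a stronger assumption than the primary model.

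At the CSP #494 missing rate the spurious difference is 1.4 to 2.7 points if missingness is both unequal and outcome-related, and 2.4 to 4.9 points if its relation to outcome differs by arm. At a 50% rate, type I error is 7.5–11% and 13.5–25% respectively. With 10% missing, the second range at a 50% rate falls from 3.1–4.8 points to 1.7–2.6. The true rates, odds ratios and arm-specific missing rates are assumptions; the documents give only the 2.45 of 3. Nothing in the documents shows that such a mechanism will occur, and the primary analysis is unaffected.

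**What to change.** In SAP II.H.2 and Protocol X.D.2, define the denominator for these outcomes as all randomised participants. Make the main analysis multiple imputation, by arm, of CAPS total score and symptom-criteria status, using baseline, mid-treatment and every available follow-up CAPS. Derive response, loss of diagnosis and remission in each imputed data set, then pool the proportions and differences. A generalised linear mixed model using all visits is an acceptable alternative.

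Keep observed-case proportions as a sensitivity table. State in SAP II.S and Protocol X.F that the non-ignorable sensitivity analyses extend to these outcomes. Missing-as-failure may be shown but should not be primary, since it can itself create a difference when missing rates differ by arm.

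The cost is a wording change and modest programming, as multiple imputation is already contemplated. The main result would rest on missing at random. Imputation removes only the bias that observed data explain, and recovery is limited for people with no follow-up CAPS, who have at most baseline and mid-treatment scores. That is why the non-ignorable analyses belong with it.

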We have also derived sample size inflation factor for more general scenarios that allow therapists to treat different numbers of participants and participants to have different numbers of post-treatment CAPS total scores. This sample size inflation factor is calculated by considering the ratio of the variance of the mean change from baseline under the mixed effect model to the variance of the mean change from baseline under the independent observations assumption, in which the mean change from baseline is computed over all individual changes from baseline at all post-treatment points from all participants. While we skip the derivation formula and results here, in the special case that each therapist treats an equal number of participants and each participant has the same number of post-treatment CAPS total score assessed at the same timepoints, the sample size formula reduces to that in the previous subsection.

C. Number of Participating Sites and Duration of Study

We will select sites that have high patient volume and at least 8 trained therapists (4 PE and 4 CPT) to deliver study treatments. Sites with research infrastructure and research experience are also preferred. Each participating site is expected to randomize 64 participants over the course of the study (8 therapists each treating 8 participants). Therefore, 14.1 sites are needed to achieve the target total randomization of 900. Because some participants are found to be ineligible for the study after signing consent (i.e. during Phase 2 or Phase 3 Screening procedures), the total number of enrolled (i.e. consented) participants in the study may be as high as 2550 (150 per site) to reach the randomization goal of 900.

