As mentioned in **Section I.E**, at present 75 sites meet the criterion of having at least 4 therapists who are proficient in PE and 4 who are proficient in CPT, and more sites are expected to qualify as the rollouts continue. **Table I.4** of **Section I.E** shows that many of these qualifying sites have more than 1500 unique PTSD outpatients in FY 2011. We anticipate a large proportion of these PTSD outpatients will be eligible for the current study because our inclusion and exclusion criteria are nonrestrictive. Even if only 5% of these patients are enrolled, a site with at least 512 PTSD patients should be able to randomize 64 patients over a 2.5-year period. We plan to recruit at 17 participating centers at the beginning of the study in case one or more centers have to be terminated.

Each participant will be treated and followed for up to 12 months and, therefore, the total duration of active recruitment, treatment and follow-up is 3.5 years. Start-up and closeout at each VA medical center will both last for 3 months. Start-up and closeout for the Study Chairs' Office, Palo Alto CSPCC and CRPCC at Albuquerque will be 6 months and 3 months, respectively. The Chairs' Office, CSPCC and CRPCC will require 12 months for final statistical analysis.

D. Final Statistical Analysis

1. Baseline comparability

Because of the large sample size of this study, we expect the randomization process to balance baseline characteristics and produce comparable groups of participants. Baseline comparability between treatment groups will be evaluated with respect to demographic and baseline physical and psychological characteristics. Summary statistics (e.g., means and standard errors for continuous variables, and frequencies and percentages for categorical variables) and graphical techniques (e.g., boxplots for continuous variables, and histograms for categorical variables), will be used to compare the baseline characteristics of the two treatment groups within study sites and the whole study. In addition, we will use t-tests to compare continuous variables and Chi square tests for categorical variables.

2. Primary objective

The primary objective is to compare the effectiveness of PE and CPT for reducing the severity of PTSD symptoms as measured by CAPS total score. The primary outcome is change of CAPS total score from baseline (pre-treatment) to the average in the six months post-treatment (measured at post-treatment and 3 and 6 months follow-up visits).

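### Response, loss of diagnosis and remission are tested by chi-square with no allowance for therapist clustering, so the nominal 5% response test runs at about 6–11%

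*SAP*

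**What the plan says.** SAP II.H.2, under the secondary analysis of the primary objective, derives response, loss of diagnosis and remission from the CAPS. It reports observed proportions with 95% confidence intervals per arm at each follow-up visit and then states: "Chi-square tests will be used to compare these outcomes between the two treatment groups". Protocol X.D.2 has the same text. Neither gives a method for the intervals, and neither names a therapist or site term.

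Protocol X.B.3 describes the structure of the data: "each therapist will deliver either PE or CPT to a number of study participants", and "observations from the participants treated by the same therapist are likely to be correlated". It multiplies the sample size by f = 1.94 for this. The primary model (Protocol X.B.1, SAP II.H.2 and II.U) has therapist as a random effect.

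Three other sentences might be read as covering the binary outcomes, but none does:

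- **SAP II.H.3** names GLIMMIX, or possibly GEE, for categorical measures among the outcomes of Table II.1. That table does not list these three, and the sentence names no therapist term.
- **SAP II.H.5** allows mixed models or GEE for therapist correlation. The sentence is optional and follows the exploratory comparisons (stable remission on the PCL, weeks to remission, sessions and hours).
- **SAP II.N** concerns repeated measures and points back to II.H.2 and II.H.3.

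**The concern.** Therapists are nested in treatment arm, so differences between therapists go directly into the treatment contrast. The three binary outcomes are cut from the same CAPS scores as the primary outcome and inherit their within-therapist correlation. A chi-square test leaves this variance out of its standard error. With no true difference between PE and CPT, it will reach p < 0.05 more often than 5% of the time.

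The plan wants the secondary results to support the primary finding and does not adjust them for multiplicity, so each nominal p-value should at least mean what it says. The treatments are expected to differ little. A false-positive difference in response or remission could be read as clinical superiority even if the continuous CAPS result, tested with the therapist term, is null.

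**Working it through.** **1. The plan's own figure.** The CSP #494 variance components in Protocol X.B.2 are therapist 36 and within-subject 174. With three post-treatment visits, τ² = 36 + 174/3 + 174 = 268, so τ = 16.4 and ρ = 36/268 = 0.134. Then n = 2(1.960 + 1.282)² × 268/25 = 225.3, or 226 per arm and 452 in total. With m = 8, f = 1 + 7 × 0.134 = 1.94, and 226 × 1.94 = 438.4, or 439 per arm and 878 in total. This matches X.B.3.

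**2. Therapist correlation at one visit.** The binary outcomes are compared visit by visit, so the three-visit ρ must be rescaled. Solving ρ = σ_P²/(σ_P² + 232) gives σ_P² = 232ρ/(1 − ρ), where 232 = 174 × 4/3. The single-visit correlation of change is σ_P²/(σ_P² + 348), where 348 = 2 × 174. Dichotomising this under a bivariate normal gives the binary intraclass correlation (ICC):

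| ρ (Table X.2) | σ_P² | Single-visit ICC | Binary ICC, 50% response | 20% or 80% | 90% |
|---|---|---|---|---|---|
| 0.10 | 25.8 | 0.069 | 0.0439 | 0.0346 | 0.0249 |
| 0.134 | 35.9 | 0.094 | 0.0596 | 0.0473 | 0.0345 |
| 0.15 | 40.9 | 0.105 | 0.0671 | 0.0535 | 0.0392 |

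The documents give no response rate; 20% to 90% is assumed.

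**3. Caseloads.** X.B.3 plans m = 8. X.C requires "at least 8 trained therapists (4 PE and 4 CPT) to deliver study treatments" and says "We plan to recruit at 17 participating centers at the beginning of the study"; with 8 therapists per site, 900/(17 × 8) = 6.6. In CSP #494 "the average number of follow-up CAPS total scores is 2.45" out of 3, and 6.6 × 2.45/3 = 5.4 observed participants per therapist at a visit.

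**4. True size of the nominal 5% test.** With f = 1 + (m − 1) × ICC, size = 2[1 − Φ(1.96/√f)].

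- Lowest: ρ 0.10, m 5.4, 90% response. f = 1 + 4.4 × 0.0249 = 1.110, size 6.3%.
- Highest: ρ 0.15, m 8, 50% response. f = 1 + 7 × 0.0671 = 1.470, size 10.6%.

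| Response, equal caseloads | m = 8 | m = 6.6 | m = 5.4 |
|---|---|---|---|
| ρ = 0.134 | 7.9–10.0% | 7.3–9.0% | 6.8–8.1% |
| ρ = 0.10 to 0.15 | 7.1–10.6% | 6.6–9.5% | 6.3–8.5% |

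Over this grid √f runs from 1.053 to 1.212. If simple binomial intervals are meant, the response intervals should be about 5% to 21% wider.

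**5. The other two outcomes.** Both are joint conditions and need more assumptions: entry score at least 45, baseline mean 70 or 80, mean drop 15 or 30. Loss of diagnosis, approximated as response plus a score below 45, has ICC 0.023–0.048 and size 6.2–9.0%. Remission, taken as response plus a score below 20, has ICC 0.007–0.035 and size 5.4–7.9%. When only about 2% remit, its size is 5.4–6.0%.

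**6. Simulation of null trials.** Equal caseloads used therapist variance 36. The modifiers assumed baseline mean 75 and mean drop 25, giving rates of about 80%, 35% and 7%, with Monte Carlo error of about 0.3 points.

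| Scenario | Response | Loss of diagnosis | Remission |
|---|---|---|---|
| m = 8 | 9.5% | 8.7% | 6.9% |
| m = 6.6 | 8.2% | 7.8% | 6.7% |
| m = 5.4 | 7.5% | 7.0% | 6.2% |
| m = 6.6, site SD 6 (assumed) | 8.1% | 7.4% | 6.6% |
| m = 6.6, 15% never start (assumed) | 7.2% | 6.8% | 6.1% |
| Unequal caseloads, mean 8, CV 0.7 (assumed) | 11.7% | 10.0% | 8.1% |
| Mildest: ρ 0.10, m 5.4, site SD 6, 15% never start | 5.7% | 5.7% | 5.2% |

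**7. Other readings of ρ.** Dichotomising ρ 0.10–0.15 without rescaling to one visit gives 6.9–12.9%. Using it directly as the binary ICC gives 10.2–17.1%. The 6–11% range is the cautious reading.

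**The case against.** The strongest objection concerns size and weight. The 10.6% needs the largest ρ in Table X.2, a caseload of 8 for every therapist and exactly 50% response. At ρ = 0.134, with 17 sites, 8 therapists each and CSP #494's missingness, response runs at 6.8–8.1%. Nor is 5.4 a floor, because X.C asks for 8 therapists or more; with 12 per site (assumed) a simulation gave 6.7%, 6.3% and 5.7% for response, loss of diagnosis and remission. The added effect of site variance is small, and in the simulations mostly within noise. Loss of diagnosis rests on a proxy, since the plan defines it by symptom criteria. All variances and score cut-offs are on the DSM-IV scale, while the trial uses the DSM-5 CAPS. Finally, these outcomes are secondary, the continuous CAPS differences are reported at the same visits, and three outcomes at three visits make nine tests with no stated multiplicity control.

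All of this stands as a limit on the figures, but none of it supplies the missing therapist term. The range is open upwards too: X.B.3 itself foresees the "possible deviation that some therapists will treat more than 8 participants", and unequal caseloads raise the error. Forgoing multiplicity adjustment accepts many tests at 5% each; it does not justify individual tests that run above 5%.

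**Conclusion.** The concern holds. As written, the three CAPS-derived binary outcomes are tested as if participants were independent, against the plan's own statement and its own treatment of the primary outcome. Over ρ 0.10–0.15 and equal caseloads of 5.4–8, the false-positive rate is 1.3 to 2.1 times nominal for response, 1.2 to 1.8 for loss of diagnosis (proxy) and 1.1 to 1.6 for remission. Unequal caseloads push it higher; non-starters and site differences push it lower, to near nominal in the mildest combination tried.

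The existence of the defect follows from the documents alone. Its exact size rests on assumed success rates, site variance and non-start rate, on caseloads derived in part by arithmetic, and on CSP #494's variances carrying over, so confidence in the figures is moderate. The primary analysis is unaffected. This should be fixed before analysis, but it does not threaten the trial's main conclusion.

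**What to change.** Replace the chi-square sentence in SAP II.H.2 and Protocol X.D.2 with a therapist-clustered comparison at each follow-up visit, and take the treatment difference and its 95% confidence interval from it. State the interval method and keep the raw proportions as description. Workable forms are:

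- **Site-adjusted risk difference.** An identity-link model with treatment and site, robust standard errors clustered on therapist, and a small-sample correction (factor G/(G − p) and G − p degrees of freedom, for G therapists and p parameters). It held 4.4–6.0% for all three outcomes in all ten simulated scenarios and tolerates sites with no remitters.
- **Unadjusted version.** A therapist-clustered risk difference, or a Rao-Scott or Donner adjusted chi-square. These held about 4.4–5.9% without site variance and were conservative (about 3–4%) with a site SD of 6.
- **GLIMMIX with an explicit therapist random effect** and marginalised differences. This is closest to methods the plan already names, but it was not simulated here.

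A logistic or GEE model with site indicators and uncorrected robust standard errors is best avoided. It ran at 5.3–7.8%, and 14–78% of remission fits failed to converge.

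The SAP also needs a rule for assigning participants who never start, or who change therapist, to a cluster; the documents have none. The cost is wording, that rule and modest programming. Intervals will be somewhat wider, and the unadjusted version loses some power if sites differ. No new data are needed.
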